7.3 Treatment Period

7.3.1 Visit 3.0 (Qualification Visit #2, Day 1, for IOP and safety measurements at 09:00 hours)

Within 2 to 7 days after Visit 2, individuals will return to the Investigator’s office for the next 09:00 hour IOP measurement.

The results of the clinical laboratory tests from Visit 1 or Visit 2 (if not performed at Visit 1) need to be available and reviewed by the Investigator. In order for the individual to be enrolled, the tests CANNOT be indicative of any clinically significant disease in the opinion of the Investigator.

The subject will be questioned regarding any changes in their health or concomitant medication use. Any change in the individual’s health status should be recorded on the Medical History page of the CRF (e.g., the subject has been diagnosed with cancer).

Inclusion/exclusion criteria will be reviewed again for the qualified individual.

The following procedures will be performed:

- Heart rate and blood pressure
- Symptomatology: Individuals will be asked “How are you feeling?”

- VFQ-25
- BCVA
- CS testing
- A non-dilated eye examination will be performed, including IOP measurements and biomicroscopy. IOP must be measured between 09:00 and 09:30 hours.

For further evaluation of OAG eyes in the study, at this time, unmedicated (post washout) IOP must be ≥ 15 mmHg and < 35 mmHg in both eyes. For further evaluation of OHT eyes in the study, at this time, unmedicated (post washout) IOP must be ≥ 22 mmHg and < 35 mmHg in both eyes. **This is the second of the four qualifying IOPs for randomization.**

Qualified individuals will continue with the measurements of IOP at 11:00 hours and 16:00 hours.

Individuals who do NOT meet the IOP requirements above may return for up to 2 additional qualification visits within 1 week of failing this qualification visit. Individuals returning at an unscheduled visit within 1 week are required to only re-measure IOP in both eyes.

Upon return for an unscheduled qualification visit, such individuals' IOP measurements would need to qualify at 09:00, 11:00, and 16:00 hours. Individuals who fail due to IOP being ≥ 35 mmHg in either eye (exclusion criterion) MAY NOT return for additional qualification visits.

Individuals are allowed to leave the Investigator's office between assessments and eat and drink with no restrictions. However, individuals are not to consume alcohol or engage in strenuous exercise.

7.3.2 Visit 3.1 (Day 1, for IOP and safety measurements at 11:00 hours)

Inclusion/exclusion criteria will be reviewed again for the qualified individual. Qualified individuals will be examined. Each examination will include:

- Symptomatology: Individuals will be asked "How are you feeling?"
- A non-dilated eye examination will be performed, including IOP measurements and biomicroscopy. IOP must be measured between 11:00 to 11:30 hours.

For further evaluation of OAG eyes in the study, at this time, unmedicated (post washout) IOP must be ≥ 15 mmHg and < 35 mmHg in the same eye. For further evaluation of OHT eyes in the study, at this time, unmedicated (post washout) IOP must be ≥ 22 mmHg and < 35 mmHg in the same eye. **This is the third of the four qualifying IOPs for randomization.**

Qualified individuals will continue with the qualification visit. Individuals who do NOT meet this requirement may return for up to 2 additional qualification visits within 1 week of failing this qualification visit. Individuals returning at an unscheduled visit within 1 week are required to only re-measure IOP in both eyes.

Upon return for an unscheduled qualification visit, such individuals would need to qualify at 09:00, 11:00 and 16:00 hours. Individuals who fail due to IOP being ≥ 35 mmHg in either eye (exclusion criterion) MAY NOT return for additional qualification visits.

Individuals are allowed to leave the Investigator's office between assessments and eat and drink with no restrictions. However, individuals are not to consume alcohol or engage in strenuous exercise.

7.3.3 Visit 3.2 (Day 1, for IOP and safety measurements at 16:00 hours)

Inclusion/exclusion criteria will be reviewed again for the qualified individual. Qualified individuals will be examined. Each examination will include:

- Symptomatology: Individuals will be asked "How are you feeling?"
- A non-dilated eye examination will be performed, including IOP measurements and biomicroscopy. IOP must be measured between 15:30 and 16:30 hours.

For further evaluation of OAG eyes in the study, at this time, unmedicated (post washout) IOP must be ≥ 15 mmHg and < 35 mmHg in the same eye. For further evaluation of OHT eyes in the study, at this time, unmedicated (post washout) IOP must be ≥ 22 mmHg and < 35 mmHg in the same eye. **This is the fourth of the four qualifying IOPs for randomization.**

Individuals who do NOT meet this requirement may return for up to 2 additional qualification visits within 1 week of failing the first qualification visit. Individuals returning at an unscheduled visit within 1 week are required to only re-measure IOP in both eyes.

Upon return for an unscheduled qualification visit, such individuals would need to qualify at 09:00, 11:00 and 16:00 hours. Individuals who fail due to IOP being ≥ 35 mmHg in either eye (exclusion criterion) MAY NOT return for additional qualification visits.

As noted in Section 4.2, subjects must qualify in both eyes based upon IOP and ocular history for a subject who qualifies; the study eye will be the eye with the higher IOP at 09:00 hours on Visit 3. If both eyes have the same IOP at 09:00 hours on Visit 3, then the right eye will be the study eye. In each subject, BOTH eyes will be treated.

At this point, eligible subjects will be randomized. The study medication kit containing 2 bottles will be dispensed to the subject, along with dosing and storage instructions by the site staff.

Subjects will be:

- Instructed to administer their masked medication OU at home between 20:00 - 22:00 hours beginning with the first dose on the evening of this study visit
- Instructed to return to the office with their study medication on Week 1 (Day 8)

For post randomization assessments, a window of ± 2 days for Visit 4 is permitted, and a window of ± 3 days for Visits 5 and 6 is permitted.

7.3.4 Visit 4.0 (Week 1 [Day 8], for IOP and safety measurements at 09:00 hours)

Subjects will return to the Investigator's office. The subject will be questioned about any missed doses and any changes in their health or concomitant medication use. Subjects will be examined, and each examination will include:

- Heart rate and blood pressure
- Symptomatology: Individuals will be asked "How are you feeling?"
- Recording of any AEs
- BCVA
- A non-dilated eye examination will be performed, including IOP measurements and biomicroscopy. IOP must be measured between 09:00 and 09:30 hours.

After randomization, any new or worsening of symptoms are to be entered as AEs.

Subjects are allowed to leave the Investigator's office between assessments and eat and drink without restrictions. However, subjects are not to consume alcohol or engage in strenuous exercise.

7.3.5 Visit 4.1 (Week 1 [Day 8], for IOP and safety measurements at 11:00 hours)

Subjects will be examined, and each examination will include:

- Symptomatology: Individuals will be asked "How are you feeling?"
- Recording of any AEs
- A non-dilated eye examination will be performed, including IOP measurements and biomicroscopy. IOP must be measured between 11:00 to 11:30 hours.

Subjects are allowed to leave the Investigator's office between assessments and eat and drink without restrictions. However, subjects are not to consume alcohol or engage in strenuous exercise.

7.3.6 Visit 4.2 (Week 1 [Day 8], for IOP and safety measurements at 16:00 hours)

Subjects will be examined, and each examination will include:

- Symptomatology: Individuals will be asked “How are you feeling?”
- Recording of any AEs.
- A non-dilated eye examination will be performed, including IOP measurements and biomicroscopy. IOP must be measured between 15:30 and 16:30 hours.

Subjects will be:

- Instructed to continue to administer their study medication at home between 20:00 - 22:00 hours (taking the daily evening dose on that day)
- Instructed to return to the office with their used study medication on Week 2 (Day 15)

7.3.7 Visit 5.0 (Week 2 [Day 15], for IOP and safety measurements at 09:00 hours)

Subjects will return to the Investigator’s office. The subject will be questioned regarding any missed doses and any changes in their health or concomitant medication use. Subjects will be examined, and each examination will include:

- Heart rate and blood pressure
- Symptomatology: Individuals will be asked “How are you feeling?”
- Recording of any AEs
- BCVA
- A non-dilated eye examination will be performed, including IOP measurements and biomicroscopy. IOP must be measured between 09:00 and 09:30 hours.

Any new or worsening of symptoms beyond those collected at baseline are to be entered as AEs.

Subjects are allowed to leave the Investigator’s office between assessments and eat and drink without restrictions. However, subjects are not to consume alcohol or engage in strenuous exercise.

7.3.8 Visit 5.1 (Week 2 [Day 15], for IOP and safety measurements at 11:00 hours)

Subjects will be examined, and each examination will include:

- Symptomatology: Individuals will be asked “How are you feeling?”

- Recording of any AEs
- A non-dilated eye examination will be performed, including IOP measurements and biomicroscopy. IOP must be measured between 11:00 to 11:30 hours.

Subjects are allowed to leave the Investigator's office between assessments and eat and drink without restrictions. However, subjects are not to consume alcohol or engage in strenuous exercise.

7.3.9 Visit 5.2 (Week 2 [Day 15], for IOP and safety measurements at 16:00 hours)

Subjects will be examined, and each examination will include:

- Symptomatology: Individuals will be asked "How are you feeling?"
- Recording of any AEs
- A non-dilated eye examination will be performed, including IOP measurements and biomicroscopy. IOP must be measured between 15:30 and 16:30 hours.

Subjects will be:

- Instructed to continue to administer their masked medication at home between 20:00 - 22:00 hours (taking the daily evening dose on that day)
- Instructed to return to the office with their study medication on Week 4 (Day 29)

7.3.10 Visit 6.0 (Week 4 [Day 29], for IOP and safety measurements at 09:00 hours)

Subjects will return to the Investigator's office. The subject will be questioned about any missed doses and any changes in their health or concomitant medication use. Subjects will be examined, and each examination will include:

- Heart rate and blood pressure
- Symptomatology: Individuals will be asked "How are you feeling?"
- Recording of any AEs
- Urine pregnancy test (tests for applicable female subjects of child bearing potential may be performed at any time point throughout Visit 6)
- Blood samples will be taken for clinical chemistry and hematology, and a urine sample will be taken for urinalysis (samples may be taken at any time point throughout Visit 6)
- BCVA

- A non-dilated eye examination will be performed, including IOP and biomicroscopy. IOP must be measured 9:00 and 9:30 hours.

All used/returned study medication kits will be collected by the site staff and returned to the Sponsor's designee for destruction.

Any new or worsening of symptoms beyond those collected at baseline are to be entered as AEs.

Subjects are allowed to leave the Investigator's office and eat and drink without restrictions. However, subjects are not to consume alcohol or engage in strenuous exercise.

7.3.11 Visit 6.1 (Week 4 [Day 29], for IOP and safety measurements at 11:00 hours)

Subjects will be examined, and each examination will include:

- Symptomatology: Individuals will be asked "How are you feeling?"
- Recording of any AEs
- A non-dilated eye examination will be performed, including IOP measurements and biomicroscopy. IOP must be measured between 11:00 and 11:30 hours.

Subjects are allowed to leave the Investigator's office and eat and drink without restrictions. However, subjects are not to consume alcohol or engage in strenuous exercise.

7.3.12 Visit 6.2 (Week 4 [Day 29], for IOP and safety measurements at 16:00 hours)

Subjects will be examined, and each examination will include:

- Symptomatology: Individuals will be asked "How are you feeling?"
- Recording of any AEs
- A non-dilated eye examination will be performed, including IOP measurements and biomicroscopy. IOP must be measured between 15:30 and 16:30 hours.
- Dilated ophthalmoscopy examination (including vertical cup-disc ratio)
- Subjects will be thanked for their participation, exited from the study, and released to the normal care of their Physician.

7.4 Observational Period

Subjects will undergo the following visits until resolution/stabilization of the cornea verticillata. Resolution of the cornea verticillata will occur when a subject has a cornea verticillata grading of zero in both eyes. Stabilization is defined as no worsening of the

cornea verticillata grading for a minimum of one year from the commencement of dosing. The duration of the observational period will vary from subject to subject.

7.4.1 OBS Visit 1 (any visit between Visits 4 to 6 when cornea verticillata is detected)

Subjects will discontinue study medication and undergo the following assessments:

- Completion of Visit 6 procedures (Exit Visit)
- Concomitant medication use
- VFQ-25
- BCVA
- CS testing
- Cornea verticillata grading

7.4.2 OBS Visits 2, 3 and 4 (3 monthly visits 1 month (30 ± 5 days) from prior OBS Visit)

At each monthly visit, the subject should be questioned regarding any changes in their health or concomitant medication use. The following procedures will be performed:

- BCVA
- Cornea verticillata grading

If cornea verticillata grading is higher than zero at this Month 1 Visit, the subject will return for a Second and/or Third Monthly Visit at which the procedures and assessments done at the first Monthly Visit will be repeated.

7.4.3 Subsequent bimonthly visits (60 days +/- 5 days from prior OBS Visit)

If at the Third Monthly Visit (OBS Visit 4) the subject has a cornea verticillata grading higher than zero, the subject will return for bimonthly (60 days +/- 5 days) visits until resolution or stabilization.

At each visit, subject will be questioned regarding any changes in their health or concomitant medication use. The following procedures will be performed:

- BCVA
- Cornea verticillata grading

7.4.4 Final Study Visit Procedures

Upon resolution or stabilization of cornea verticillata at any OBS Visit, subjects will be questioned regarding any changes in their health or concomitant medication use. The following procedures will be performed and the subject will exit the study:

- VFQ-25
- BCVA
- CS testing
- Cornea verticillata grading

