Randomized subjects will dose the assigned investigational product in both eyes QD in the evening (between 20:00 and 22:00 hours) beginning on Day 1 and up to and including the evening prior to the final visit at Visit 6 (Week 4). Procedures conducted at each of study Visits 4-6 will include safety measures and efficacy measurements, including IOP assessments. At Visits 4-6 (Weeks 1, 2, and 4, respectively), IOP will be assessed at 09:00, 11:00 and 16:00 hours. Following completion of the Visit 6 (Week 4) study visit procedures, subjects will exit the study. For subjects who discontinue early, every possible effort will be made to assure there is a final visit that includes all examinations listed for Visit 6.0 (Week 4) and dilated ophthalmoscopy.

For subjects who show any evidence of cornea verticillata by slit lamp examination using the grading system for amiodarone keratopathy (Orlando 1984) during the 28-day treatment period, the assigned study medication will be discontinued, all exit visit procedures (Visit 6) will be completed and subject will be followed in an observational period starting as OBS Visit 1 (Day 1) in which subjects will undergo VFQ-25, BCVA testing, CS testing and cornea verticillata grading. All subjects with cornea verticillata will return for monthly surveillance visits (OBS Visit 2, 3 and 4) where they will undergo BCVA testing and cornea verticillata grading for 3 months. If cornea verticillata persists at the 3-month time point

(OBS Visit 4), subjects will return every 2 months for BCVA testing and cornea verticillata grading until resolution or stabilization. Resolution is defined as grading of zero of the cornea verticillata grading and stabilization is defined as no worsening of the cornea verticillata grading for a minimum of one year from the commencement of dosing. Once resolution or stabilization is confirmed in both eyes, the subject will undergo VFQ-25, BCVA testing, CS testing and exit the study.

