3.2 Rationale for Study Design and Control Group

In order to further evaluate the hypotensive efficacy of netarsudil ophthalmic solution relative to its placebo in subjects with OAG or OHT and to generate additional safety data for netarsudil in Japanese population, a double-masked, parallel group, 4-arm active- and placebo-controlled study design was selected.

As the intended route of administration for netarsudil ophthalmic solution is topical ocular, this is the route to be used in this study. The dosage regimen selected for this study is based on a previously completed Phase 2 study (AR-13324-CS201) and 4 completed Phase 3 studies (AR-13324-CS301, AR-13324-CS302, AR-13324-CS303, and AR-13324-CS304).

A Phase 1 study (AR-13324-CS104) evaluating the ocular and systemic safety of 2 concentrations of netarsudil (0.02% and 0.04%) ophthalmic solution compared to placebo over a 7-day period was conducted in healthy volunteers of Japanese ethnicity within the second generation in the United States. However, efficacy results with netarsudil ophthalmic solution to date have been generated in a mostly non-Japanese population. In order to ensure that similar results are observed in Japanese subjects, this study is being conducted in subjects in Japan.

The design of the observational period for subjects who develop cornea verticillata during the study is based on an observational study conducted in the United States in a non-Japanese population (AR-13324-OBS01). Per discussion at PMDA meeting, long term follow-up is necessary in order to understand the impact on visual function and resolution of cornea verticillata in Japanese population.

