6.20.3 Actions after Discontinuation

All subjects who discontinue study medication due to a report of an AE must be followed and provided appropriate medical care until their signs and symptoms have remitted or stabilized or until clinically meaningful abnormal laboratory findings have returned to acceptable or pre-study limits.

For subjects who choose to withdraw consent or who are discontinued for non-compliance prior to completing the treatment period, every possible effort should be made by the Investigator to assure there is a final visit that includes all examinations listed for Visit 6.0 (Exit) and dilated ophthalmoscopy.

For subjects who discontinue study medication due to cornea verticillata, subjects will complete Exit Visit (Visit 6) procedures and will be followed in an observational period until resolution/stabilization of the cornea verticillata. Subjects will not be treated with any investigational product during this observational period. They may, however, continue treatment with IOP-lowering agents or other topical ocular medications (Rx or OTC) as recommended by their eye care provider/practitioner.

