5. Ocular symptoms: Subjects will be queried at each visit “How are you feeling?” and treatment emergent AEs beginning at Visit 4 will be documented on the AE form. Additional symptoms reported after screening and before randomization will be documented on the medical history form. Adverse events will be recorded for every study visit (i.e., at 09:00, 11:00, and 16:00 hours) as needed.
6. Individuals returning at an Unscheduled Visit within 1 week to re-attempt IOP qualification are required to only re-measure IOP in both eyes.
7. Gonioscopy evaluation up to 3 months prior to randomization is acceptable.
8. Pachymetry within 1 week prior to screening is acceptable.
9. Entry visual field evaluation up to 3 months prior to randomization is acceptable. Visual field collection must meet the requirement for automated threshold visual field assessment (e.g., 30-2 or 24-2 Humphrey) and reliability.
10. Collect kit(s) dispensed during the Day 1 visit.

Observational Period

Study Procedures	OBS Visit 1 (Day 1) Visit when cornea verticillata is diagnosed	OBS Visits 2-4 Monthly Visit x3 (30 ± 5 days if Cornea Verticillata Persist)	OBS Visit 5 and up Bi-monthly Visits after 3 rd Monthly visit (60 ± 5 days if Cornea Verticillata Persist)	Final Visit if Resolution/ Stabilization of Cornea Verticillata ^{1,2} is confirmed
Discontinuation of IP	X			
Conmed Review	X	X	X	X
Symptoms/ Assessment of Ocular and General Health	X	X	X	X
VFQ-25	X			X
Best Corrected Visual Acuity	X	X	X	X
Contrast Sensitivity	X			X
Cornea Verticillata Grading	X	X	X	X

¹. Should have a grading score of zero OU or stabilization confirmed to exit the study.

². If cornea verticillata grading is zero at any visit, or stabilization of cornea verticillata is confirmed, the subject completes outlined procedures listed in Final Visit and exits the study.

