10.3 Visual Function Questionnaire (VFQ-25)

The VFQ-25 is a reliable and valid 25-item version of the 51-item National Eye Institute Visual Function Questionnaire that measures subjective assessment of patient-reported vision-targeted health status elements that are most important to people with eye disease. All subjects will undergo VFQ-25 at Visit 3 (Qualification #2, Day 1, 09:00) in the treatment period. For observational period, the VFQ-25 data will be collected at OBS Visit 1 and Final Visit.

The VFQ-25 sub-scale scores and composite score will be calculated as the steps below.

Table 15-1 Step 1: Recoding of Items

Question Numbers	Original Item Score ^(a)	Recoded Value
1, 3, 4, 15c ^(b)	1	100
	2	75
	3	50
	4	25
	5	0
2	1	100
	2	80
	3	60
	4	40
	5	20
	6	0
5, 6, 7, 8, 9, 10, 11, 12, 13, 14, 16, 16a, A3, A4, A5, A6, A7, A8, A9	1	100
	2	75
	3	50
	4	25
	5	0
	6	*
17, 18, 19, 20, 21, 22, 23, 24, 25, A11a, A11b, A12, A13	1	0
	2	25
	3	50
	4	75
	5	100
A1, A2	0 to 10	0 to 10

^(a)Precoded response choices as printed in the questionnaire.

^(b)Question 15c has four-response level, but is expended to a five-levels using question 15b.

Note: If 15b=1 then 15c should be recoded to 0.

If 15b=2, then 15c should be recoded to missing.

If 15b=3, then 15c should be recoded to missing.

*Response choice "6" indicates that the person does not perform the activity because of non-vision related problems. If this choice is selected, the item is coded as "missing".

Table 15-2 Step 2: Averaging Items to Generate VFQ-25 Sub-Scales

Sub-Scale	Number of items	Items to be averaged (after recoding per Table 15-1)
General Health	1	1
General Vision	1	2
Ocular Pain	2	4, 19
Near Activities	3	5, 6, 7
Distance Activities	3	8, 9, 14
Vision Specific:		
Social Functioning	2	11, 13
Mental Health	4	3, 21, 22, 25
Role Difficulties	2	17, 18
Dependency	3	20, 23, 24
Driving	3	15c, 16, 16a
Color Vision	1	12
Peripheral Vision	1	10

The subject's sub-scale score is the average of scores from non-missing items. The higher scores indicate better vision-specific health-related quality of life. The subject's composite VFQ-25 score is the average of all sub-scale scores except for the general health item.

The VFQ-25 sub-scale scores and composite score will be summarized using the continuous summary statistics for Visit 3.

A subject listing of VFQ-25 sub-scale and composite scores will also be produced.

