16.1 Visual Function Questionnaire

The subjects who develop cornea verticillata will undergo VFQ-25 at OBS Visit 1 (when cornea verticillata is diagnosed) and the final visit. The scores and the score changes from OBS Visit 1 will be summarized using the continuous summary statistics by treatment group.

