16.3 Contrast Sensitivity Testing

The CS testing will undergo at OBS Visit 1 (when cornea verticillata is diagnosed) and the final visit. The CS results will be summarized at eye level using discrete summary statistics for each spatial frequency by treatment group, and by whether or not the corneal verticillata deposit event is ongoing at given visit. The numeric part of the CS results will be summarized at eye level using the continuous summary statistics.

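### A subject who leaves the observational period before cornea verticillata resolves or stabilizes has no scheduled VFQ-25 or contrast sensitivity after OBS Visit 1

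*Protocol*

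**What the plan says.** - **Trigger for the repeat tests.** Protocol 7.4.4 lists VFQ-25, BCVA, CS and grading "Upon resolution or stabilization of cornea verticillata at any OBS Visit". The Appendix 1 footnote sets the same condition for leaving: "Should have a grading score of zero OU or stabilization confirmed to exit the study".
- **Meaning of stabilization.** In Protocol 3.1, "stabilization is defined as no worsening of the cornea verticillata grading for a minimum of one year from the commencement of dosing". A stabilized subject may therefore still have a grade above zero.
- **Visits in between.** Protocol 7.4.2 (OBS Visits 2 to 4) and 7.4.3 (bimonthly visits) list only BCVA and grading as procedures.
- **SAP timing.** SAP 10.3 states that "the VFQ-25 data will be collected at OBS Visit 1 and Final Visit", and SAP 10.4 says the same for CS. SAP 16.1 and 16.3 agree: "The subjects who develop cornea verticillata will undergo VFQ-25 at OBS Visit 1 (when cornea verticillata is diagnosed) and the final visit"; "The CS testing will undergo at OBS Visit 1 (when cornea verticillata is diagnosed) and the final visit".
- **Planned summaries.** Protocol 9.7.2 plans change from the initial assessment for CS and BCVA by eye, split by whether the event is ongoing, with VFQ-25 handled similarly by subject. SAP 16.1 summarizes change in VFQ-25 from OBS Visit 1. SAP 16.3 keeps the ongoing-or-not split for CS.

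**The concern.** Protocol 3.2 gives the reason for the observational period: "long term follow-up is necessary in order to understand the impact on visual function and resolution of cornea verticillata in Japanese population". VFQ-25 and CS are two of its three visual-function measures. If both are repeated only once the deposits have cleared or have been followed without worsening to one year, then whether a subject has a follow-up score depends on the course of the condition under study. Someone who withdraws or is lost while deposits persist supplies an OBS Visit 1 value and nothing to compare it with. So does someone whose grade is worsening, until one of the two conditions is met. The reported change then describes the subjects who reached an endpoint, not everyone who developed verticillata.

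**Working it through.** The plan gives no figure on this point, so the check is of the text and the visit calendar.

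**1. What each visit collects (Protocol 7.4 and the Appendix 1 observational table)**

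| Visit | BCVA | Grading | VFQ-25 | CS |
|---|---|---|---|---|
| OBS Visit 1 | yes | yes | yes | yes |
| OBS Visits 2–4 | yes | yes | no | no |
| Bimonthly visits | yes | yes | no | no |
| Final Visit (resolved or stabilized) | yes | yes | yes | yes |
| Leaving before either condition | none written | none written | none written | none written |

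**2. Does another provision fill the last row?**
- Protocol 6.20.3 requires a final visit "For subjects who choose to withdraw consent or who are discontinued for non-compliance prior to completing the treatment period". That does not reach the observational period. Protocol 6.20.2 is likewise tied to the treatment period.
- Protocol 3.1 has a general sentence on early discontinuation. Even if it is stretched to cover observation, it calls for the Visit 6.0 examinations plus dilated ophthalmoscopy. The Visit 6.0 list (Protocol 7.3.10 and Appendix 1) contains neither VFQ-25 nor CS.
- Protocol 6.12 and 6.13 mention further testing of subjects with verticillata but fix no visit.
- An unscheduled visit (Protocol 7.5) would not help, because SAP 8.5 leaves unscheduled visits out of the analysis unless they serve as baseline.
- No missing-data rule is given for VFQ-25 or CS in this period.

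**3. How long a subject is exposed to the gap**

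Inputs: OBS Visit 1 falls on nominal Day 8, 15 or 29; then three visits 30 ± 5 days apart; then visits 60 ± 5 days apart. One year from first dose on Day 1 is Day 366. The stabilization visit is the first scheduled visit on or after Day 366.

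Nominal spacing, starting from Day 8:
- OBS Visit 4 is on Day 8 + 3 × 30 = 98.
- Four bimonthly visits reach Day 98 + 240 = 338, which is too early.
- Five reach Day 98 + 300 = 398.
- The gap from OBS Visit 1 is 398 − 8 = 390 days.

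| OBS Visit 1 | All visits 5 days early | Nominal | All visits 5 days late |
|---|---|---|---|
| Day 8 | Day 413 (405 days) | Day 398 (390 days) | Day 373 (365 days) |
| Day 15 | Day 420 (405 days) | Day 405 (390 days) | Day 380 (365 days) |
| Day 29 | Day 379 (350 days) | Day 419 (390 days) | Day 394 (365 days) |

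The gap is therefore about 13 months at nominal spacing, and 350 to 405 days across these cases. Mixing early and late visits would move it somewhat in either direction. A subject who resolves sooner exits sooner and is scored.

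**4. What selection could do (assumed inputs)**

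Let u be the share of subjects who do not resolve and w the share of those who leave before stabilization. If all resolved subjects are scored, the resolved share among subjects with a Final Visit score is (1 − u) / [(1 − u) + u(1 − w)].

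| u | True resolved share | w = 0.2 | w = 0.5 | w = 1.0 |
|---|---|---|---|---|
| 0.1 | 90% | 91.8% | 94.7% | 100% |
| 0.3 | 70% | 74.5% | 82.4% | 100% |
| 0.5 | 50% | 55.6% | 66.7% | 100% |

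Worked case: 0.7 / (0.7 + 0.3 × 0.8) = 0.745. With w = 0 there is no shift. The table shows who is scored, not a bias in VFQ-25 or CS. A bias also needs the scores of early leavers to differ from the rest, and the documents give neither u, nor w, nor the score change by status.

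**The case against.** Several counter-arguments have weight.

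- **BCVA is complete by design.** It is taken at every observational visit, so visual function as a whole does not go unmeasured. This stands, and it limits the point to VFQ-25 and CS.
- **Persisting deposits alone do not cause a missing score.** A reader might infer that anyone who exits with deposits goes unscored. The documents do not support that: stabilized subjects can exit with deposits and do have the Final Visit tests. They also supply some later event-ongoing values for the planned split, though only at about one year.
- **The loss would be visible.** Early leavers keep their OBS Visit 1 values, summaries report n, and disposition and individual scores are listed for this period (SAP 16, Table 14.4.1, Listings 16.3.1, 16.3.4 and 16.3.6). This also stands. Visibility shows how many scores are missing but does not recover them.
- **The group is small and the summaries are descriptive.** The 16.7% once-daily incidence in Protocol 1.1, applied to 3 × 52 = 156 active-arm subjects, gives about 26. Onset there ran from 2 to 13 weeks, against 28 days of dosing here, so the number may be lower. No test or success criterion depends on these scores.
- **Earlier experience was reassuring.** Protocol 1.1 reports no clinically meaningful effect on visual function in the previous observational study. That makes a large bias less likely, but Protocol 3.2 still asks the question anew for Japanese subjects.
- **SAP Table 3-2 may contradict the point.** As extracted, it marks VFQ-25 and CS in all four columns. The table is visibly broken, and SAP 10.3, 10.4, 16.1 and 16.3 and Protocol Appendix 1 all say otherwise. If the marks are real, the gap shrinks to subjects who leave before OBS Visit 2.

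**Conclusion.** The gap is real and narrow. As written, a subject who leaves the observational period before resolution or stabilization has no scheduled VFQ-25 or CS after OBS Visit 1, and change in these two measures is reported only for resolved or stabilized subjects. With persistent, non-worsening deposits, the exposure lasts about 13 months.

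A reader might go further and conclude that the reported change is shown to be tilted toward recovery, or might compound the 5% discontinuation allowance in Protocol 9.2 over the follow-up to put a number on the tilt. The documents support neither. The direction is plausible, but no text says why subjects would leave or how their scores would differ. The 5% is a sample-size allowance for the trial with its 28-day treatment period. Carrying it into off-drug follow-up has no basis, and compounding it to a year ignores subjects who clear and exit with a score. The size of any bias cannot be computed.

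The conclusion assumes that the Table 3-2 marks are an extraction fault. It also assumes that the text of Protocol Amendment 1 still applies. The SAP is written to Amendment 2, which is not among the documents, so the absence of an exit rule there is unconfirmed. The point does not touch the efficacy conclusions. It is worth correcting because the affected measures serve the stated purpose of this period and the correction is cheap.

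**What to change.** 1. **Protocol 6.20.3, 7.4.4 and the Appendix 1 observational table.** Ask a subject who leaves the observational period before resolution or stabilization to complete the Final Visit assessments (VFQ-25, BCVA, CS and grading) at exit.
2. **SAP 16.1 and 16.3.** Report these scores as a separate category, *early exit, event ongoing*, beside resolved and stabilized, and give the number of subjects with no follow-up score. State that the category is not merged under SAP 8.5, which otherwise combines early-termination with end-of-study visits in by-visit safety summaries.
3. **SAP Table 3-2.** Reconcile it with SAP 10.3, 10.4, 16.1 and 16.3 and with Protocol Appendix 1 on when VFQ-25 and CS are collected.

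The cost is one protocol sentence, a schedule footnote and one table row, using tests already planned for the same subjects. Some withdrawing or lost subjects will not attend, so the gap is reduced but not closed.
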